## **8.11.      Impact of COVID-19 Pandemic**

Missed visits due to COVID-19 are captured on the CRFs and/or as protocol deviations. Summaries and analyses to describe and/or assess the impact of the COVID-19 pandemic will be included in the clinical study report. These may include tabulations of COVID-19 related protocol deviations and patterns of missing data, summaries of COVID-19 AEs, the addition of a per-protocol population, and comparative analyses of selected endpoint before, during and after the pandemic.

# **9.            IDENTIFICATION AND SUMMARY OF PROTOCOL DEVIATIONS**

Important protocol deviations are pre-specified in the study Protocol Deviation Management Plan. In accordance with ICH E3 (1995), important eligibility deviations per the inclusion/exclusion criteria (documented on study CRFs) and important post-randomization protocol deviations (tracked in study clinical trial management system, CTMS) will be identified and listed separately by study center and subject. Important deviations will be summarized for

the ITT population by deviation code (a standardized description e.g. “did not satisfy eligibility criteria” or “received prohibited medication”) and deviation category (a standardized severity classification: “important” or “not important”).

## **10. DATA QUALITY ASSURANCE**

The Clinical, Data Management, Biostatistics, and Medical Writing departments at Exelixis and designees will work diligently and collaboratively to ensure that the data collected and analyzed for this study are of the highest quality. In addition to electronic evaluation of the data and verification of data from source documents at the respective sites, a data review meeting will be held to review the data and correct significant data anomalies before the study database is locked or data are extracted for the purpose of analysis.

## Appendix A: Date Imputation Rules

### Incomplete Cancer Diagnosis Date

If *year* is missing (or completely missing): do not impute

If only *day* is missing: set to 15th of the month.

If *day* and *month* are missing: set to July 1st.

If either imputation rule above results in a diagnosis date > informed consent:  
set diagnosis date to the date of informed consent - 1.

### Incomplete Adverse Event Onset Date

Assumption: For on-study Adverse Events.

If *year* is missing (or completely missing): set to the date of first dose.

If (*year* is present and *month* and *day* are missing) or (*year* and *day* are present and *month* is missing):

If *year* = *year* of first dose: set the date to the first dose date.

If *year* < *year* of first dose: set *month* and *day* to December 31st.

If *year* > *year* of first dose: set *month* and *day* to January 1st.

If *month* and *year* are present and *day* is missing:

If *year* = *year* of first dose, and:

If *month* = *month* of first dose: set *day* to day of first dose.

If *month* < *month* of first dose: set *day* to last day of *month*.

If *month* > *month* of first dose: set *day* to 1st day of *month*.

If *year* < *year* of first dose: set *day* to last day of month.

If *year* > *year* of first dose: set *day* to 1st day of month.

For all other cases: set to date of first dose.

Do not impute start/stop dates for incomplete prior radiation, prior surgery/procedures, prior transfusions, and prior concomitant medications.

### Incomplete Start Date for prior and concomitant medication and prior anticancer therapy.

If *year* is missing (or completely missing): do not impute.

If (*year* is present and *month* and *day* are missing) or (*year* and *day* are present and *month* is missing):

Set *month* and *day* to January 1st.

If *year* and *month* are present and *day* is missing:

Set *day* to 1st day of month.

### Incomplete Concomitant Medication End Date

If *year* is missing (or completely missing): do not impute.

If (*year* is present and *month* and *day* are missing) or (*year* and *day* are present and *month* is missing):

Set *month* and *day* to December 31st.

If *year* and *month* are present and *day* is missing:

Set *day* to last day of the month.

### Incomplete Concomitant and Subsequent Anticancer Therapy Start Date,

Assumption: Anticancer therapies reported on the Subsequent Anticancer Therapy CRF.

If *year* is missing (or completely missing): set to date of last dose of study treatment + 1

If (*year* is present and *month* and *day* are missing) or (*year* and *day* are present and *month* is missing):

If *year* > year of the last dose: Set *month* and *day* to January 1st.

If *year* = year of the last dose: Set *month* and *day* to date of last dose of study treatment + 1

If *year* and *month* are present and *day* is missing:

Set *day* to 1st day of month if the resulting imputed date is greater than date of last dose or if the month is before the month of last dose date and year is same or before the year of the last dose date. Otherwise set the imputed date to date of last dose + 1

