hepatobiliary (hepatitis [2], cholangitis [1], drug-induced liver injury [1], hepatotoxicity [1], immune-mediated hepatitis [1]), investigations (ALT increased [1], AST increased [1]), pneumocystis jirovecii infection (1), pneumonia (1), rash (1), thrombocytopenia (1), myocardial infarction (1), and ischemic stroke (1). The most common AEs overall among these 44 subjects were fatigue (9) or asthenia (7), ALT increased (10), rash (10), nausea (8), decreased appetite (8), diarrhea (8), mucosal inflammation (8), hepatotoxicity (7), AST increased (7), palmar-plantar erythrodysaesthesia (7), cough (6), dysgeusia (6), and myalgia (6). AEs leading to treatment discontinuation were reported in 9 (20.5%) of the 44 subjects, including ALT increased (4), AST increased (3), amylase increased (1), blood alkaline phosphatase (ALP) increased (1),  $\gamma$ -glutamyltranspeptidase (GGT) increased (1), lipase increased (1), drug-induced liver injury (1), hepatitis (1), hepatotoxicity (1), diarrhoea (1), asthenia (1) and ischemic stroke (1).

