3. **Bone scans:** Technetium bone scans (TBS) should be performed at screening for all subjects. After randomization, bone scans will be performed in subjects with known bone metastases and otherwise as clinically indicated per standard of care. Any soft tissue lesions associated with identified bone lesions must be imaged by CT/MRI and assessed in alignment with the CAP assessments. Bone scan findings alone cannot be used for the determination of progression or response and need to be corroborated by CT or MRI (which will be used as the basis for RECIST evaluations).

The same imaging modalities used at screening are to be used for subsequent tumor assessments after randomization. If there is clinical concern regarding the administration of any contrast, then a non-contrast CAP imaging study is acceptable as a screening assessment if it clearly demonstrates measurable disease per RECIST 1.1 that can be followed without the need for contrast. If at a follow up imaging time point the use of contrast is prohibited (eg, due to acquired impaired renal function or contrast allergy) then the same modality should be used without contrast.

Tumor assessments should continue on the protocol-defined schedule, relative to the date of randomization, regardless of whether study treatment is given, reduced, held or discontinued.

Radiographic response and PD will be determined using RECIST 1.1. Investigators are encouraged, if any doubt or ambiguities exist about radiographic progression, to continue study treatment if the subject is tolerating it acceptably, repeat radiographic tumor imaging at the next scheduled time point, and delay determination of progression until the findings indicating radiographic progression are unequivocal. Radiographic progression determined by the

CONFIDENTIAL

Protocol XL184-313 Protocol Amendment 3.0  
Page 72 of 193

Investigator does not necessarily warrant discontinuation of tumor assessments or study treatment.

Radiographic tumor assessments are to continue until the following criteria are met:

- For subjects who discontinue study treatment upon determination of Investigator-assessed radiographic PD per RECIST 1.1, tumor assessments may cease.
- For subjects who discontinue study treatment before Investigator-assessed radiographic PD, tumor assessments are to continue per the protocol-defined schedule until Investigator-assessed radiographic PD per RECIST 1.1.

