### 9.2.2.1 Primary Analysis: Progression-Free Survival

The primary analysis of PFS is event-driven and will be conducted after at least 249 events have been observed in the PITT population (see [Section 9.1.2](#)). It is designed to include only progression events as determined by the BIRC per RECIST 1.1. Clinical deterioration or radiographic progression determined by the Investigator will not be considered progression events.

General censoring rules for the primary analysis of PFS are described below:

- Subjects who receive systemic NPACT or surgical resection of target tumor lesion(s) before experiencing an event will be right censored at the date of the last tumor assessment prior to the date of initiation of subsequent therapy or surgery.
- Subjects who have not experienced an event (and are not otherwise censored) at the time of data cutoff will be right censored on the date of their last tumor assessment.
- Subjects who miss 2 or more scheduled tumor assessments followed by an event will be right censored on the date of their most-recent tumor assessment prior to the missing assessments.

Hypothesis testing between the two treatment arms will be performed using the stratified log-rank test with a 2-sided 0.05 level of significance. The stratification factors are those used to stratify the randomization (see [Section 3.4](#)).

The median PFS and the associated 95% CI for each treatment arm will be estimated using the Kaplan-Meier method. The HR with 95% CIs will be estimated using a Cox regression model and will include the same stratification factors described above.

In the primary analysis of PFS, if the p-value for the stratified log-rank test is statistically significant and the HR ( $\lambda_{\text{cabozantinib + nivolumab/ipilimumab}} / \lambda_{\text{nivolumab/ipilimumab+placebo}}$ ) is  $< 1$ , the null hypothesis of no difference between the two treatment arms in PFS will be rejected and it will be inferred that PFS is superior in the group receiving cabozantinib plus nivolumab/ipilimumab compared with the group receiving nivolumab/ipilimumab plus placebo.

Analyses of PFS based upon investigator assessment will follow the same methods.

CONFIDENTIAL

Protocol XL184-313 Protocol Amendment 3.0  
Page 126 of 193

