### 4.1. Definition of Baseline

In general, for efficacy endpoints the last observed measurement prior to randomization will be considered the baseline measurement. An exception to this rule is the efficacy biomarkers such as pharmacogenetics blood samples and plasma biomarker samples. These samples per schedule of assessment are to be collected on Week 1 Day 1 (W1D1) (which could be up to 3 days after randomization) but prior to the administration of the first dose; hence baseline for these measurements will be defined with respect to the first dose date. For subjects who did not take any study treatment, any biomarker sample available prior to randomization will be considered as the baseline observation.

For safety endpoints the last observation on or before first dose of study treatment will be considered the baseline measurement unless otherwise specified and will be established for each period defined in [Section 4.5](#).

For assessments on the day of first dose of study treatment where time is not captured, if such procedures are required by the protocol to be conducted before first dose or a nominal pre-dose indicator is available, this will serve as sufficient evidence that the assessment occurred prior to first dose.

The earliest instance of administration of any agent of study treatment will be considered as the time point of first dose. Similarly, the latest instance of administration of any agent of study treatment will be considered as the time point of last dose of study treatment.

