#### **4.4. Missing and Partial Data**

In general, other than for partial dates, missing data will not be imputed and will be treated as missing. The algorithms for imputation of partial dates vary depending upon the parameter.

Data imputation rules are presented in [Appendix A](#).

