**Table 8: Event and Censoring Rules for Primary and Sensitivity Analyses**

Estimand	Primary		Primary		Primary	
Analysis type	Primary		Sensitivity		Sensitivity	
Analysis purpose	Primary		Evaluate assessment time bias		Evaluate assessor bias	
Analysis ID	PFS-EP-1		PFS-EP-2		PFS-EP-3	
Analysis name	rPFS per BIRC		Uniform dates		rPFS per Investigator	
Estimand endpoint	Radiographic PD		Radiographic PD		Radiographic PD	
Population	PITT		PITT		PITT	
Situation	Outcome	Date of Outcome	Outcome	Date of Outcome	Outcome	Date of Outcome
Radiographic PD per RECIST 1.1 per BIRC	event	date of recorded PD	event	date of scheduled visit (or next scheduled visit if between visits)	NA	NA
Radiographic PD per RECIST 1.1 per Investigator	NA	NA	NA	NA	event	date of recorded PD
Death	event	date of death	event	date of death	event	date of death
Intercurrent events (excluding those with Treatment Policy strategy for all estimands)						
Clinical deterioration	NA	NA	NA	NA	NA	NA
Systemic NPACT (medications)	censored	date of last ATA* before first initiation of therapy	censored	date of last ATA* before first initiation of therapy	censored	date of last ATA* before first initiation of therapy
Local NPACT (medications)	NA	NA	NA	NA	NA	NA
Surgical resection of target tumor lesion(s)	censored	date of last ATA* before target lesion resection	censored	date of last ATA* before target lesion resection	censored	date of last ATA* before target lesion resection
Local radiation: to soft tissue for disease under study	censored	date of last ATA* before local radiation of soft tissue for disease under study	censored	date of last ATA* before local radiation of soft tissue for disease under study	censored	date of last ATA* before local radiation of soft tissue for disease under study
Missing data						
No baseline ATA	censored	date of rand.	censored	date of rand.	censored	date of rand.
≥ 2 consecutive missing scheduled ATA immediately prior to analysis event	censored	date of last ATA* before missing visits	censored	date of last ATA* before missing visits	censored	date of last ATA* before missing visits
Observation ongoing						
None of the above criteria for event or censoring	censored	date of last ATA*	censored	date of last ATA*	censored	date of last ATA*

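### For subjects who stopped all study treatment before progression, SAP Appendix A can date subsequent anticancer therapy ahead of a BIRC progression that actually came first, turning a primary PFS event into a censoring

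*SAP*

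**What the plan says.** **Imputation (SAP Appendix A, concomitant and subsequent anticancer therapy start date).**

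- Day missing: the 1st "day of month if the resulting imputed date is greater than date of last dose", or the 1st if the therapy month precedes the last-dose month. For the remaining cases: "Otherwise set the imputed date to date of last dose + 1".
- Day and month missing: last dose + 1 if the year is that of last dose; 1 January if the year is later.
- Year missing: last dose + 1.

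Last dose is defined across all agents, including the daily oral one (SAP 4.1): "the latest instance of administration of any agent of study treatment will be considered as the time point of last dose".

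**Use in PFS.** For the primary analysis PFS-EP-1, Table 8 censors a subject who receives systemic NPACT at the "date of last ATA* before first initiation of therapy". Protocol 9.2.2.1 limits this to subjects who receive NPACT "before experiencing an event will be right censored at the date of the last tumor assessment". PFS-EP-2 and PFS-EP-3 follow the same rule. Duration of response (SAP 7.5.3) and best overall response (SAP 7.5.1) take their censoring from these analyses.

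**Scope of the imputation.** SAP 4.4 says "In general, other than for partial dates, missing data will not be imputed and will be treated as missing", and points to Appendix A. SAP 4.6 gives inclusion in summary tables as the purpose of imputing therapy dates.

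**Progression off drug is expected.** Protocol 5.7.6.1: "For subjects who discontinue study treatment before Investigator-assessed radiographic PD, tumor assessments are to continue per the protocol-defined schedule".

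**The concern.** Whether a BIRC progression counts as an event depends on whether NPACT came before it. Appendix A places a partial NPACT date by reference to last dose alone. For a subject who left all study treatment, stayed on the scan schedule, progressed and then started second-line therapy, last dose says little about when that therapy began, while the progression date says a good deal. The rule can therefore put the therapy before the progression that prompted it.

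The affected subject moves from an event at progression to a censoring at the previous adequate scan, or at randomization if there was none. A censoring created this way is tied to having progressed, so it is informative. The SAP does use a clinical anchor elsewhere: its partial death date rule refers to the date last known alive, which includes the last radiographic assessment.

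**Working it through.** **1. The plan's own figures.** Inputs from Protocol 9.5: HR 0.66, two-sided alpha 0.05, 90% power, 1:1 allocation, 249 events.

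- Schoenfeld: 4 × (1.960 + 1.282)² / (ln 0.66)² = 244 events. Freedman gives 251. The stated 249 lies between them.
- Power at 249 events: Φ(√249 × 0.4155 / 2 − 1.96) = 0.906.
- Critical HR: exp(−2 × 1.96 / √249) = 0.780, as stated.

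**2. The rule applied.** Progression (PD) on 15 March, NPACT truly on 25 March, day missing:

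| Last dose | Imputed NPACT start | Primary PFS outcome |
|---|---|---|
| 20 February | 1 March | censored |
| 10 March | 11 March | censored |
| 14 March | 15 March (tie) | event kept |
| 15 March | 16 March | event kept |
| 18 March | 19 March | event kept |

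Both branches can fail: the 1st of the month in the first row, last dose + 1 in the second. If NPACT truly began in April, the event is kept.

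**3. All combinations in a 31-day month.** PD on any day, NPACT later in the same month, last dose before NPACT and no more than 60 days before PD:

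| Last dose | Events turned into censorings |
|---|---|
| on or after PD | 0 of 4,960 |
| one day before PD | 0 of 465 |
| in the month, at least 2 days before PD | 4,060 of 4,060 |
| before the month | 21,605 of 23,375 |

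The 1,770 exceptions in the last row are PDs on the 1st. These are calendar combinations, not probabilities. Outside the table, NPACT recorded in a month before the last-dose month also goes to the 1st. Protocol 7.2 prohibits NPACT before permanent discontinuation, so this should be rare.

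**4. Same-month condition.** With a gap of G days from PD to NPACT, the chance that both fall in one calendar month is about 1 − G/30.4375: 0.77, 0.54, 0.31 and 0.08 at 7, 14, 21 and 28 days, and zero from 31 days. The documents give no gap.

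**5. Size of the shift.** Scans are every 8 weeks through Week 50, then every 12 (Protocol 5.7.6.1), so a day-only case usually moves back about 8 or 12 weeks. With the month missing, the start goes to last dose + 1 or to 1 January, and the displacement of the NPACT date can approach 12 months in the January case.

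**6. Number of events.** Assumptions, none from the documents: NPACT starts in the PD month for 10–30% of events, the day is missing for 2–10% of these, and all study treatment had stopped before PD for 20–40%.

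- Low: 249 × 0.10 × 0.02 × 0.20 = 0.1
- High: 249 × 0.30 × 0.10 × 0.40 = 3.0

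**7. Power and time.** If events were lost and not replaced, power would be 0.904 at 247 events, 0.901 at 244 and 0.895 at 239. SAP 7.1.5 waits for 249 events, so losses cost time instead. At the pace in SAP 4.8.1 (about 12 events in 7 months), one event takes 7/12 = 0.58 month. That pace is for the first 440 subjects; the population has since been widened to 550.

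**The case against.** **The link to PFS is not stated.** SAP 4.6 speaks of summary tables, and neither 7.1.4 nor Table 8 says that imputed NPACT dates drive censoring. This stands as a limit: the link is an inference from 4.4. But no other rule exists for a partial NPACT date in PFS, and the supplementary analyses PFS-EA1 to EA3 use the NPACT date itself as an event date, so a complete date is needed. If Appendix A does not apply, a primary censoring date has no rule, which also needs correcting.

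**Other analyses cover these subjects.** Partly true, and it would be wrong to infer that the primary result is unprotected. As Table 9 reads, PFS-EP-12 reclassifies subjects censored for NPACT as events in both arms, and PFS-EP-14 does so in the triplet arm. PFS-EA2 and EA3 count NPACT as an event. However, all four date the event at the imputed start, EA2 and EA3 address different estimands, and EP-12 and EP-14 reclassify other censored subjects at the same time. None isolates the imputation.

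**The remedy uses the outcome to date an intercurrent event.** True: it resolves every day-only ambiguity as an event and can give one subject different NPACT dates in the BIRC and Investigator analyses. That is tolerable over a span of less than a month. It is less so when only the year is known, so those dates need different handling.

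**Conclusion.** The defect is real but narrow. It needs three things together: all study treatment stopped at least two days before progression, a partial NPACT date whose possible range includes the progression, and use of Appendix A dates for censoring. Under the assumptions shown, about 0.1 to 3 of 249 events are affected by missing days. Power is not at risk.

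Three stronger readings are tempting and are not supported:

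- *That missing days generally go to the 1st and so drop events.* The branch is conditional, and a subject dosed up to or past progression in that month, or until the day before, keeps the event.
- *That a missing month in the year of last dose makes the loss certain.* If the last dose was on or after progression, last dose + 1 falls after it and the event is kept.
- *That the bias favors the triplet.* Protocol 1.6 reports of an earlier triplet arm that "AEs leading to treatment discontinuation were reported in 9 (20.5%) of the 44 subjects". That figure has no comparator and does not show that all agents stopped; Protocol 3.6.1 allows one component to continue without another. A difference between arms in stopping everything before progression would bias the comparison, but its direction is not established.

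The correction is worth making because it is cheap and protects the classification of the primary endpoint.

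**What to change.** 1. State in SAP 4.4 or 7.1.4 that Appendix A dates feed the censoring for PFS, duration of response and best overall response.
2. Add to Appendix A: when only the day of the NPACT start is missing and a recorded progression falls in the same month, use the later of the current imputed date and progression date + 1. Take progression from the BIRC for PFS-EP-1 and EP-2, and from the Investigator for PFS-EP-3.
3. For dates with the month or year missing, keep the current rule. List the subjects whose event or censoring status depends on the imputation, and repeat PFS-EP-1 with the latest possible start date as a sensitivity analysis.

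In the first two rows of the example, item 2 gives 16 March and restores the event. The cost is a short addition to the SAP text, one programming condition, a listing and one extra run. The downside is that a progression that truly followed NPACT in the same month would count as an event. The 249-event target and the power do not change.
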